**Table 1. Study Flow Chart – Screening and Treatment Period (Day -34 to Day 29)**

Protocol Activity	Screening	Treatment						
		Day 1	Day 2 PK/PD Blood Draw	Day 4 PK/PD Blood Draw	Day 8	Day 15	Day 22	Day 29
Visit Identifier	Screening							
Visit window relative to end of Day 1 IP administration	Day -34 to Day 0		-6 hours/+1 day	-6 hours/+ 1 day	±1 day	±2 days	±2 days	±2 days
Factor VIII and Factor IX inhibitor levels (for subjects with a hemophilia history of inhibitor only)	X k							
CD4 cell count								
Prothrombin 20210 mutation testing	X							
Factor V Leiden mutation testing	X							
Lipid profile f	X							
Protein C activity/Protein S level	X							
Serology: HBs Ag, HBc Ab, HCV Ab and HIV	X							
Banked biospecimens (Prep D1)		X						
TFPI level		X g	X	X	X	X	X	X
PT/INR	X	X			X	X	X	X
aPTT	X	X			X	X	X	X
Fibrinogen	X	X			X	X	X	X
Anti-thrombin III	X	X			X	X	X	X
Thrombin Generation (TGA)		X g	X	X	X	X	X	X
Prothrombin fragment 1+2 (PF1+2)		X g	X	X	X	X	X	X
D-dimer		X g	X	X	X	X	X	X
Dilute prothrombin time (dPT)		X g	X	X	X	X	X	X
Cardiac Troponin I		X			X	X	X	X
PK blood sampling		X g	X	X	X	X	X	X g

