- One sample will be drawn prior to IP administration for both the subcutaneous (SC) and intravenous (IV) routes of administration. For IV administration only, collect a second sample from the arm not used for IV IP administration immediately (0 to 5 minutes) following completion of the IV infusion and line flush.
- Treatment assignment may occur at any time prior to dosing once subject has met all eligibility criteria.
- IP is administered at these visits for cohorts with SC administration only.

- j. Subject diary dispensed and/or collected. Subject diary is reviewed, including information about study compliance bleeding assessments (including site and traumatic/spontaneous) and injection site reactions. At Day 1, subjects will be provided training with respect to filling out the diary including timing and nature of information to be entered.
- k. FVIII and FIX inhibitor levels must be determined by a local laboratory. A positive inhibitor test result will be above the upper limit of normal for the assay. Inhibitor test results from up to 6 months prior to Day 1 may be used to meet this requirement.

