### **3.1. Planned Number of Subjects**

Approximately 24 subjects are planned for enrollment at approximately 20 study sites. Subjects who are withdrawn for reasons other than safety may be replaced at the discretion of the Sponsor. Subjects with inhibitors to FVIII or FIX will only be enrolled into a cohort with a dose level and regimen that was previously assessed as safe and well tolerated in subjects without inhibitors. Additional subjects and/or cohorts may be enrolled in the event that the number of dosing cohorts or size of dosing cohorts is increased to fully define the dose range and/or clinical profile at the respective dose levels.

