##### **4.1. Inclusion Criteria**

Subject eligibility should be reviewed and documented by an appropriate member of the investigator's study team before subjects are included in the study.

Subjects must meet all of the following inclusion criteria to be eligible for enrollment in the study:

1. Evidence of a personally signed and dated informed consent document indicating that the subject (or a legally acceptable representative/parent(s)/legal guardian) has been informed of all pertinent aspects of the study.
2. Males  $\geq 18$  and  $< 65$  years of age.
3. Body Mass Index (BMI)  $\geq 17.5$  and  $\leq 30.5$  kg/m^2 and total body weight  $\geq 50$  and  $\leq 100$  kg.
4. Diagnosis of severe hemophilia A or B (Factor VIII or Factor IX activity  $\leq 1\%$ ).
5. Subjects enrolled as Factor VIII or Factor IX inhibitor patients must have a positive inhibitor test result (above the upper limit of normal) at the local laboratory and must receive a bypass agent as primary treatment for bleeding episodes. A positive inhibitor test result will be above the upper limit of normal for the assay. Inhibitor test results from up to 6 months prior to Day 1 may be used to meet this requirement.
6. Patients with an episodic (on-demand) treatment regimen prior to Screening, who are willing and able to washout from Factor VIII (for at least 72 hours) or Factor IX (for at least 96 hours) replacement therapy, or bypass agent therapy (for rFVIIa and APCC: at least 72 hours), prior to Screening laboratory assessments of factor activity and have no plans to institute prophylactic factor treatment during the study period.

7. Had at least 6 acute bleeding episodes (spontaneous/traumatic) during the 6-month period prior to Screening. Surgical bleeding episodes do not apply to this criterion.
8. If receiving therapy for human immunodeficiency virus (HIV) or active hepatitis infection, have stable disease and be on a stable regimen at the time of study entry (ie, stable dosing for at least 3 months before consent).
9. Willing and able to comply with scheduled visits, treatment plan, laboratory tests, and other study procedures.
10. If with partners currently pregnant or if able to father children, agree to use a highly effective method of contraception throughout the study and for least 28 days after the last dose of investigational product.

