## 6. STUDY PROCEDURES

### 6.1. Screening

Subjects will be screened within 35 days prior to administration of the investigational product to confirm that they meet the subject selection criteria for the study. The investigator (or an appropriate delegate at the investigator site) will obtain informed consent from each subject in accordance with the procedures described in the [Subject Information and Consent](#) section.

All screening procedures must be repeated for any subject who failed initial screening procedures and is re-screening into the study, with the exception of the following labs related to genetic mutation screening or pharmacogenomics samples:

- Prothrombin 20210 mutation testing;
- Factor V Leiden mutation testing;
- Banked biospecimens;
- Factor VIII and Factor IX activity;
- Factor VIII or Factor IX inhibitor (this test is only required for subjects with a hemophilia history of inhibitors).

The following procedures will be completed during Screening:

- Obtain written informed consent;
- Review Inclusion and Exclusion criteria;
- Obtain medical history, including hemophilia history and inhibitor history, and collect the number of bleeding episodes over the past 6 months;
- Obtain complete medication history of all prescription or nonprescription drugs, and dietary and herbal supplements taken since the start of Screening;
- Review use of Factor VIII or Factor IX replacement therapy, or bypass agent therapy, to ensure subject meets washout criteria prior to Screening;
- Collect demography and height;
- Collect weight;

- Provide instructions regarding study contraception requirements;
- Obtain pulse rate, respiratory rate, oral temperature, and supine blood pressure;
- Conduct full physical examination (PE). On and after Day 1 and at the discretion of the investigator, limited physical examinations based on signs and symptoms will be performed, if clinically indicated, to assess changes from baseline/previous visits of any ongoing symptoms;
- Collect single 12-lead ECG. If ECG is abnormal, collect triplicate ECG.
- Collect blood specimens for the following for analysis at a local laboratory, if necessary:
  - Factor VIII or Factor IX inhibitor (this test is only required for subjects with a hemophilia history of inhibitors). Inhibitor test results from up to 6 months prior to Day 1 may be used to meet this requirement.

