**Table 5. Laboratory Tests**

Hematology	Chemistry	Urinalysis	Other
Hemoglobin Hematocrit RBC count Platelet count WBC count Total neutrophils (Abs) Eosinophils (Abs) Monocytes (Abs) Basophils (Abs) Lymphocytes (Abs)	BUN/urea and Creatinine Glucose (fasting) Calcium Sodium Potassium Chloride Total CO 2 (Bicarbonate) AST, ALT Total Bilirubin Alkaline phosphatase Uric acid Albumin Total protein	pH Glucose (qual) Protein (qual) Blood (qual) Ketones Nitrites Leukocyte esterase Urobilinogen Urine bilirubin Microscopy a	Factor V Leiden mutation b Prothrombin 20210 Mutation b HBs Ag b Total HbcAb b HCVAb b HIV b Anti-thrombin III Protein C activity b Protein S level b PT/INR aPTT Fibrinogen Cardiac Troponin I Factor VIII c Factor IX c Factor VIII and Factor IX inhibitor d Lipid profile b CD4 cell count b
	Additional Tests (Needed for Hy's law)		
	AST, ALT (repeat) Total bilirubin (repeat) Albumin (repeat) Alkaline phosphatase (repeat) Direct bilirubin Indirect bilirubin Creatine kinase GGT PT/INR		

- Only if urine dipstick is positive for blood, protein, nitrites or leukocyte esterase.
- At Screening only.
- At Screening and Day 1 only.
- Only At Screening and only for subjects with hemophilia history of inhibitors, if necessary. Inhibitor test results from up to 6 months prior to Day 1 may be used to meet requirement.

Any remaining serum/plasma from samples collected for clinical safety labs at baseline and at all times post-dosing may be retained and stored for the duration of the study. Upon completion of the study, retained safety samples may be used for the assessment of CCI [REDACTED] samples to be used for this purpose will be packaged and shipped to Pfizer's BioBank for storage. These data will not be included in the clinical study report. Samples will be retained in Pfizer's Biobank for up to 1 year following completion of the study.

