**Table 6. Blood Volume for SC Cohorts**

Sample Type	Sample Volume (mL)	Number of Sampling Times			Total Volume (mL)
		Screening	Study Period	Follow-Up	
Safety Labs					157
Serum chemistry (with Lipid profile a )	5	1	7	1	45
Hematology	3	1	7	1	27
Prothrombin 20210 mutation	3	1	0	0	3
Factor V Leiden mutation testing	3.5	1	0	0	3.5
aPTT, PT/INR, Anti-thrombin III b , Factor VIII and Factor IX activity c , Fibrinogen, Protein C a , Protein S a , D-dimer, PF1+2 (PD samples) [Single combined sample]	4.5	1	11	1	58.5
Serology (HBs Ag, HBc Ab, HCV Ab, and HIV)	5	1	0	0	5
Cardiac Troponin I d	3	0	5	0	15
PK	4.5	0	11	1	54
Immunogenicity (ADA, NAb)	9	0	5	1	54
PD (note some PD assayed from safety samples)					106.8
TFPI level	2.7	0	11	1	32.4
TGA	3.5	0	11	1	42
dPT	2.7	0	11	1	32.4
Factor VIII and Factor IX inhibitor a	4.5	1	0	0	4.5
CCI [REDACTED]	[REDACTED]	[REDACTED]	[REDACTED]	[REDACTED]	[REDACTED]
Banked biospecimens	4	0	1	0	4
TOTAL					393.8

a at Screening only.

b at Screening and Days 1, 8, 15, 22 and 29 only.

c at Screening and Day 1 only.

d at Days 1, 8, 15, 22 and 29 only.

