### **9.2. Efficacy Analysis**

#### **9.2.1. Analysis of the Efficacy Endpoint**

ABR will be calculated and summarized descriptively by dose level. ABR will also be summarized by inhibitor status, overall and by dose level and may be evaluated by factor deficiency (Factor VIII vs Factor IX).

The ABR will be analyzed using a Poisson regression model with over dispersion, if appropriate. The model based ABR and upper and lower 80% CI will be presented. The details will be included in the SAP.

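### Inhibitor-free status is not confirmed by laboratory test in subjects with no known inhibitor history, although the Section 3.1 safeguard and the by-status tables rely on it

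*Protocol*

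**What the plan says.** Three places in the protocol decide who has an inhibitor test.

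- Table 1 (Schedule of Activities) has a row, marked at Screening only, for "Factor VIII and Factor IX inhibitor levels (for subjects with a hemophilia history of inhibitor only".
- Section 6.1 says "this test is only required for subjects with a hemophilia history of inhibitors".
- The footnote to Table 5 reads "Only At Screening and only for subjects with hemophilia history of inhibitors, if necessary".

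Footnote k to Table 1 assigns the test to a local laboratory and calls a result positive when it lies above the assay's upper limit of normal. It also accepts older results: "Inhibitor test results from up to 6 months prior to Day 1 may be used to meet this requirement".

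Inclusion criterion 5 (Section 4.1) states: "Subjects enrolled as Factor VIII or Factor IX inhibitor patients must have a positive inhibitor test result". It adds that these subjects must use a bypass agent as their main bleed treatment. Sections 4.1 to 4.3 contain no counterpart requiring a negative result, and the exclusion criteria do not name inhibitor status.

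The status is then relied on:

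- Section 3.1 admits subjects with inhibitors only to "a dose level and regimen that was previously assessed as safe and well tolerated in subjects without inhibitors".
- Section 9.2.1 says "ABR will also be summarized by inhibitor status, overall and by dose level".
- Section 9.6 presents abnormal safety findings separately for inhibitor subjects.
- SAP Section 6.5.1 splits adverse events by inhibitor status where applicable.
- SAP Section 3.4 lists inhibitor status among the hemophilia-history items collected at screening, but gives no rule for deriving it.

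**The concern.** The protocol demands laboratory proof that an inhibitor is present but none that it is absent. Being without inhibitors is the condition under which a new regimen is first assessed, and the protocol neither defines it nor requires a test for it in a subject whose history is silent.

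Two things are at stake. First, the sponsor's own safeguard in Section 3.1 can fail without anyone breaking a written rule, because nobody would know that the subject had an inhibitor. Second, an inhibitor-positive subject can be counted as inhibitor-free in the bleeding-rate and safety summaries by status. With 6 subjects per cohort, one such subject is 1/6 = 17% of a cohort.

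**Working it through.** The plan states no figure on this point, so there is none to reproduce. The check is a trace through the text, followed by an illustration.

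**Trace.** Take a subject who has an inhibitor but no recorded history of one.

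1. *Screening history (Section 6.1).* Inhibitor history is taken from every subject. His is negative.
2. *Screening laboratory (Table 1, Section 6.1, Table 5).* The test is tied to a positive history, so it is not done.
3. *Factor activity.* This is measured in everyone at Screening and Day 1. Inclusion criterion 4 requires 1% or less from all subjects, so a qualifying value does not separate those with inhibitors from those without.
4. *Eligibility (Sections 4.1 to 4.3).* Criterion 5 applies only to subjects enrolled as inhibitor patients. Nothing else asks for a result.
5. *Cohort entry (Section 3.1).* He is treated as without inhibitors and may enter a regimen at its first use.
6. *Reporting.* SAP Section 6.1 derives hemophilia A or B from a laboratory value. Inhibitor status has no such rule, so he appears in the non-inhibitor rows.
7. *Efficacy decision (SAP Sections 5.1 and 5.2.3).* The decision rule and the negative binomial model work by dose cohort against the historical group. Inhibitor status is not a term in either, so this step is unaffected.

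**Illustration.** Let p be the share of no-history subjects with an unrecognised inhibitor. The documents give no value, so p is assumed. Cohort size is n = 6 (protocol Section 9.1). Subjects are taken as independent and all 6 as having no inhibitor history. The chance of at least one is 1 − (1 − p)^6.

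| Assumed p | Calculation | Chance of at least one in 6 |
|---|---|---|
| 1% | 1 − 0.99^6 | 5.9% |
| 2% | 1 − 0.98^6 | 11.4% |
| 5% | 1 − 0.95^6 | 26.5% |

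If some of the 6 have a history and are tested, the exponent and the chance both fall.

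**Blood volume.** Table 6 has a row for "Factor VIII and Factor IX inhibitor" at 4.5 mL, taken once at Screening, and Table 7 has the same. Their totals are 393.8 mL (SC) and 433.2 mL (IV). The text of Section 7.7 gives 389.3 and 428.7 mL. The differences are 393.8 − 389.3 = 4.5 and 433.2 − 428.7 = 4.5. The tables therefore already allow for this sample, and the text does not.

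**The case against.** The strongest reply is that reliance on history is a reasonable design choice. Every subject's inhibitor history is reviewed, and anyone with a history is tested or has a recent result. These are adults on on-demand treatment with at least 6 bleeds in 6 months, and Section 1.2 notes that inhibitors make factor replacement less effective. An inhibitor that matters clinically would often be known already. This stands as a reason to expect a low rate. It does not close the gap, because a history cannot reveal an inhibitor that nobody has recognised.

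It is also fair to say that the effect on the analysis is limited, since status enters only descriptive splits. That stands in full.

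Four stronger readings are tempting, and the documents do not support them.

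- *A reader might infer that inhibitor status goes wholly unchecked.* It does not: history is taken from all, and those with a history are tested. What is missing is laboratory confirmation in the rest.
- *A reader might infer that a known test-positive subject treated with factor, who does not satisfy criterion 5, could properly enter a first-time regimen as a non-inhibitor subject.* Section 3.1 restricts any subject with inhibitors, however enrolled, so that would breach it. The Protocol Summary and Section 3 also describe the inhibitor population as users of bypass agents. At most, criterion 5 is loosely worded.
- *A reader might infer that the gap biases the historical comparison.* SAP Section 6.2.1.1 compares every dose cohort with one control group, filtered on age and factor activity and not separated by inhibitor status. A correctly identified inhibitor subject meets the same comparison, so the test would change nothing there.
- *A reader might extend the illustration to all 24 subjects.* The Section 3.1 condition works at the first use of a regimen, and some of the 24 may have an inhibitor history and be tested. The cohort of 6 is the relevant unit.

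**Conclusion.** The point holds in a limited form. In subjects without a known inhibitor history, inhibitor-free status rests on history alone, while a written safeguard and several planned tables depend on it. The consequence is possible exposure of an unrecognised inhibitor subject to a first-time regimen, and misplacement in descriptive by-status rows. The cohort-level efficacy conclusion does not depend on it.

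The 6% to 26% range for a cohort of 6 rests wholly on the assumed 1% to 5%, on independence, and on all 6 having no inhibitor history. It shows scale and is not an estimate for this trial. That the testing rule leaves a gap follows from the text and does not depend on the rate. The change is worth making mainly because it is cheap.

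**What to change.** 1. **Protocol Section 4.1, Table 1 (row and footnote k), Section 6.1 and Table 5.** For every subject enrolled as without inhibitors, require a documented negative inhibitor result (not above the assay's upper limit of normal) from the 6 months before Day 1. This is the window that footnote k already allows.
2. **SAP Section 3.4.** Define the inhibitor-status variable from that laboratory result, and use it for all summaries by status.
3. **Protocol Section 7.7.** Align the text totals (389.3 and 428.7 mL) with Tables 6 and 7 (393.8 and 433.2 mL). The text also says that the total collected should not increase, so it should start from the figure that includes the sample.
4. **SAP Section 2.2 and protocol Section 3.1.** The SAP places inhibitor subjects in whichever cohorts are open, without the Section 3.1 condition. The two passages must be reconciled.

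**Cost.** One 4.5 mL local test, drawn at the existing Screening visit and only where no result from the past 6 months exists. The downside is an occasional screen failure, or reassignment of a subject found to be positive.

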**Table 1. Study Flow Chart – Screening and Treatment Period (Day -34 to Day 29)**

Protocol Activity	Screening	Treatment						
		Day 1	Day 2 PK/PD Blood Draw	Day 4 PK/PD Blood Draw	Day 8	Day 15	Day 22	Day 29
Visit Identifier	Screening							
Visit window relative to end of Day 1 IP administration	Day -34 to Day 0		-6 hours/+1 day	-6 hours/+ 1 day	±1 day	±2 days	±2 days	±2 days
Immunogenicity (ADA, NAb)		X				X		X
CCI		Ⓢ				Ⓢ		Ⓢ
Inclusion/exclusion criteria review	X	X						
Treatment assignment h		X						
Investigational Product administration		X			X i	X i	X i	X
Subject diary j		X			X	X	X	X
Collect information on new bleeding episodes	X	→	→	→	→	→	→	→
Monitoring infusion/injection site reactions		X	→	→	→	→	→	→
Adverse event monitoring	X	→	→	→	→	→	→	→
Concomitant treatments	X	→	→	→	→	→	→	→

Abbreviations: → = ongoing/continuous event; ADA = anti-drug antibodies; aPTT = activated partial thromboplastin time; ECG = electrocardiogram; HBc Ab = hepatitis B core antibody; HBs Ag = hepatitis B surface antigen; HCV Ab = hepatitis C antibody; HIV = human immunodeficiency virus; hr = hours; IP = investigational product; N/A = not applicable; NAb = neutralizing antibodies; PK = pharmacokinetic; PT/INR = prothrombin time/international normalized ratio; TFPI = tissue factor pathway inhibitor

- A full physical examination (PE) will be conducted during Screening. On and after Day 1 and at the discretion of the Investigator, limited examinations based on signs and symptoms will be performed, if clinically indicated to assess changes from baseline/previous visits of any ongoing symptoms.
- Instructions will be provided at Screening and at Follow-up/End of Study visit; contraception check will be performed at other visits. A longer duration of contraception usage may be required if data from B7841002 warrant this change.
- Vital signs to be assessed include pulse rate, respiratory rate, oral temperature, and supine blood pressure.
- Triplicate ECG required at Day 1. Single ECG required at additional time points unless ECG is abnormal, in which case a triplicate ECG is required.
- Differential hematology panel required at Days 1, 29, 85 and 113.
- Subjects must be fasting for 12 hours prior to blood draw.
- One sample will be drawn prior to IP administration for both the subcutaneous (SC) and intravenous (IV) routes of administration. For IV administration only, collect a second sample from the arm not used for IV IP administration immediately (0 to 5 minutes) following completion of the IV infusion and line flush.
- Treatment assignment may occur at any time prior to dosing once subject has met all eligibility criteria.
- IP is administered at these visits for cohorts with SC administration only.

- j. Subject diary dispensed and/or collected. Subject diary is reviewed, including information about study compliance bleeding assessments (including site and traumatic/spontaneous) and injection site reactions. At Day 1, subjects will be provided training with respect to filling out the diary including timing and nature of information to be entered.
- k. FVIII and FIX inhibitor levels must be determined by a local laboratory. A positive inhibitor test result will be above the upper limit of normal for the assay. Inhibitor test results from up to 6 months prior to Day 1 may be used to meet this requirement.

**Table 2. Study Flowchart – Treatment and Follow-up Period (Day 30 to Day 113)**

Protocol Activity	Treatment										Follow-up/End of Study f
	Day 30 PK/PD Blood Draw	Day 33 PK/PD Blood Draw	Day 36 (SC Cohort)	Day 43 (SC Cohort)	Day 50 (SC Cohort)	Day 57	Day 64 (SC Cohort)	Day 71 (SC Cohort)	Day 78 (SC Cohort)	Day 85	
Visit Window relative to end of Day 29 IP administration	-6 hours/+1 day	-6 hours/+1 days	±2 days	±2 days	±2 days	±2 days	±2 days	±2 days	±2 days	±2 days	±7 days
Physical examination a						X				X	X
Weight						X				X	X
Contraception instructions/check b						X				X	X
Vital Signs c						X				X	X
Urinalysis						X				X	X
Serum chemistry						X				X	X
Hematology d						X				X	X
TFPI level	X	X				X				X	X
PT/INR						X				X	X
aPTT						X				X	X
Fibrinogen						X				X	X
Thrombin Generation (TGA)	X	X				X				X	X
Prothrombin fragment 1+2 (PF1+2)	X	X				X				X	X
D-dimer	X	X				X				X	X
Dilute prothrombin time (dPT)	X	X				X				X	X
PK blood sampling	X	X				X e				X	X
Immunogenicity (ADA, NAb)						X				X	X f
CCI											
Investigational Product administration			X g	X g	X g	X	X g	X g	X g		

